8.3.4 CLASSIFICATION OF AN ADVERSE EVENT

8.3.4.1 SEVERITY OF EVENT

In addition to determining whether an AE fulfils the criteria for an SAE or not, the severity of AEs experienced by participants will be recorded in accordance with the Common Terminology Criteria for Adverse Events (CTCAE) v5.0, published 27 November 2017.

The severity of AEs will be graded as follows should there be no CTCAE grading available for a specific AE:

- Grade 1: Mild; asymptomatic or mild symptoms; clinical or diagnostic observations only; intervention not indicated.
- Grade 2: Moderate; minimal, local or non-invasive intervention indicated; limiting age-appropriate instrumental activities of daily living.
- Grade 3: Severe or medically significant but not immediately life-threatening; hospitalisation or prolongation of hospitalisation indicated; disabling; limiting self-care activities of daily living.
- Grade 4: Life-threatening consequences; urgent intervention indicated.
- Grade 5: Death related to AE.

A mild, moderate, or severe AE may or may not be serious. These terms are used to describe the intensity of a specific event. Medical judgement should be used on a case-by-case basis.

Seriousness, rather than severity assessment, determines the regulatory reporting obligations.

8.3.4.2 RELATIONSHIP TO STUDY INTERVENTION

The Principal Investigator or delegate must assess the relationship of each event to the malaria challenge agent, IMP (MMV367), the definitive antimalarial medications, and other trial procedures (separately) and decide whether, in their medical judgement, there is a reasonable possibility that the event may have

been caused by any of the trial interventions. Where possible, a distinction should be made between events considered related to the malaria challenge agent, MMV367, and the definitive antimalarial medications.

If there is no valid reason for suggesting a relationship, then the AE should be classified as “not related”. Alternatively, if there is any valid reason for suspecting a cause-and-effect relationship between the study intervention and the occurrence of the AE (even if undetermined or untested), then the AE should be considered as “related” to whichever product is relevant. This should be documented in the participant’s clinical file (source data) and eCRF.

The following may guide this assessment:

Related/suspected:

The temporal relationship between the event and the study intervention is compelling and/or follows a known or suspected response pattern to that product, and the event cannot be explained by the participant’s medical condition, other therapies or accident.

Not related/not suspected:

The event can be readily explained by other factors such as the participant’s underlying medical condition, concomitant therapy or accident and no plausible temporal or biologic relationship exists between the study intervention and the event.

In addition to the assessments of relationship to the trial interventions, the Investigator should comment on the AE record in the eCRF whether an AE is related to the trial participation of the participant (trial procedures etc.).

Of note, a sign or symptom associated with malaria infection that is of expected intensity, frequency and duration for the individual participant in the context of this trial is considered to be a malaria challenge agent-related event.

8.3.5 TIME PERIOD AND FREQUENCY FOR EVENT ASSESSMENT AND FOLLOW-UP

All AEs must be documented and followed up during the study by the Investigator until the event is resolved.

Events that are unresolved at the time of the participant’s last follow-up visit should continue to be followed up by the Investigator until no further medically relevant information in relation to the event can be expected and the Investigator considers it justifiable to terminate the follow-up. The participant will be referred to a general practitioner or medical specialist as appropriate. The Sponsor retains the right to request additional information for any participant with ongoing AE(s)/SAE(s) at the end of the trial, if judged necessary.

All AEs should be treated appropriately. The Investigator will decide upon the appropriate action to be taken in response to an AE, which may include one or more of the following:

- no action taken (i.e., further observation only), or
- administration of a concomitant medication, or
- hospitalisation or prolongation of current hospitalisation (event to be reported as an SAE), or
- other.

8.3.6 ADVERSE EVENT REPORTING

It is the Investigator's responsibility to document and report all AEs occurring in the clinical trial whether spontaneously reported by the participant, observed by the Investigator (either directly or by laboratory or other assessments), or elicited by general questioning. The period of observation for collection of AEs extends from the time of inoculation with the malaria challenge agent to EOS. These AEs must be recorded on specific AE pages of the eCRF. Events reported prior to this will be recorded as medical history, unless the symptoms worsen during the trial.

The following information should be recorded for all AEs:

- Description
- Dates and times of onset and resolution
- Seriousness (SAE or not)
- AESI (yes/no)
- Severity
 - If severity of an AE changes, only one AE will be reported, with the highest severity recorded in the eCRF and listings and tables. In the clinical file (source data), the description of the AE will report the various severities observed over time.
 - If the AE resolves and then reoccurs, then two AEs will be reported.
- Action taken in response to the AE (including treatment given).
- Outcome.
- Relationship to the trial treatments or procedures (causality assessment), including the IMP, malaria challenge agent, definitive antimalarial medications, or any other treatment or procedure conducted during the trial.

8.3.7 SAE AND AESI REPORTING

The Investigator will take immediate appropriate action in response to SAEs and AESIs to ensure participant safety and in an attempt to identify the cause of the event. The Investigator must notify the SAE or AESI to the pharmacovigilance provider (Prime Vigilance) by email within 24 hours of becoming aware of the event.

All reports must be signed by the Principal Investigator or delegate and notified to Prime Vigilance preferably by email or fax to:

Email: [contact]

Back-up [contact]

Prime Vigilance Contact:

Head Office: [name]

Any copies of participant's medical records provided for SAE or AESI reporting must have all participant identifiers redacted before submission.

The report forms will always be completed as thoroughly as possible with all available details of the event and signed by the Principal Investigator or delegate. If the Principal Investigator or delegate does not have all information regarding an event, they will not wait to receive additional information before reporting the event. A follow-up SAE or AESI report should be completed within 14 days, or if there is no new information the report form should be updated when additional information is received.

The Principal Investigator or delegate will always provide an assessment of causality at the time of the initial report.

Email transmission of the report forms is the preferred method to transmit this information to Prime Vigilance. In rare circumstances notification by telephone is acceptable, with a copy of the report form sent by overnight mail.

The Principal Investigator or delegate, or responsible person according to local requirements, will comply with the applicable local regulatory requirements related to the reporting of SAEs to regulatory authorities and the HREC. Any SAE that meets the criteria of a SUSAR will be reported to the TGA by the Sponsor in accordance with the Sponsor's reporting procedures.

8.3.8 REPORTING EVENTS TO PARTICIPANTS

Not applicable.

8.3.9 REPORTING OF PREGNANCY

Pregnancy itself is not defined as an AE/SAE. Any complication or termination of pregnancy for medical reasons are to be reported as an AE/SAE. Spontaneous abortion, still birth or congenital anomaly must be reported as an SAE. Any WOCBP enrolled in the study who becomes pregnant during the study and the following 34 days after MMV367 administration should be followed through delivery or termination of the pregnancy. This has been calculated based on 30 days (one female menstrual cycle) plus 5 half-lives of the IMP. Five half-lives have been calculated as 4 days.

The Investigator will collect pregnancy information and report to Prime Vigilance within 24 hours of becoming aware of a participant's pregnancy using the pregnancy form and following the same process as described in section 8.3.5 for SAEs. Pregnancy follow-up should be recorded on the same form including pregnancy outcomes.

Once pregnancy is confirmed, pregnant female participants will be immediately withdrawn from the study and will be managed as per section 7.2. Where possible, the Investigator will also attempt to collect and report information regarding pregnancy outcomes of female partners of any male participants who were administered MMV367 in this study and the following 94 days after MMV367 administration. This has

been calculated based on 90 days (one cycle of spermatogenesis) plus 5 half-lives of the IMP. Five half-lives have been calculated as 4 days. Appropriate signed informed consent will be required directly from the pregnant female partner to obtain and report this information. Any participant's female partner who becomes pregnant during the study should be followed through delivery or termination of the pregnancy.

9 STATISTICAL CONSIDERATIONS

The following sections describe the statistical analysis as it is foreseen when the study is being planned. A detailed Statistical Analysis Plan (SAP) and Modelling Analysis Plan (MAP) will be finalised and approved prior to study conduct. The SAP and MAP will provide details of all analyses to be performed as well as the format of listings and tables to be provided for completion of the Clinical Study Report (CSR). Any deviations from the SAP will be described and justified in the final CSR.

9.1 STATISTICAL HYPOTHESES

The primary objective of this study is to characterise the PK/PD relationship of MMV367 in healthy participants experimentally infected with blood stage *P. falciparum*. There is no pre-specified statistical hypothesis for testing this objective.

9.2 SAMPLE SIZE DETERMINATION

A maximum sample size of up to 18 participants is expected to be sufficient to achieve the primary endpoint of the study, which is to determine the PK/PD parameters of MMV367. This sample size is not based on formal statistical calculations but rather is based on previous experience of characterising the PK/PD relationship of antimalarials using the IBSM model [3, 11]. The specific number of participants required will be dependent on the emerging results during the study; it is possible that less than 18 participants will be required. The SDRT will review the data after the completion of each cohort and decide when sufficient data has been obtained to complete the primary endpoint. No more than 18 participants will be administered IMP in this study.

9.3 POPULATIONS FOR ANALYSES

At minimum, two populations will be used for data analyses, the Full Analysis Set (FAS) and the IMP Set. The FAS will consist of all enrolled participants (i.e. those inoculated with the malaria challenge agent on Day 0). The IMP set will consist of all enrolled participants who receive the IMP on Day 8.

The FAS will be used to assess all participant disposition, baseline, demographic and protocol deviation data. Safety data may be assessed using both the FAS and IMP sets, as specified in the SAP.

Additional populations for analysis of PK, PD and PK/PD parameters will be defined in the SAP.

The number of participants in each analysis set will be summarised, with a corresponding listing.

9.4 STATISTICAL ANALYSES

9.4.1 GENERAL APPROACH

Continuous variables will be summarised with the number of observations (non-missing values), mean, standard deviation (SD), median, quartiles, minimum and maximum. The minimum and maximum values will be presented to the same number of decimal places as recorded in the raw data. The mean, median and SD will be presented to one more decimal place than the raw data. Categorical variables will be summarised with the number of observations and the numbers and percent from each category. Percentages will be rounded to one decimal place, with the denominator being the number of participants in the relevant population with non-missing data. No missing data will be imputed. If required, confidence intervals (CIs) will be two sided and will use 95% confidence levels. Any analyses requiring significance testing will use a two-sided test at the 5% significance level.

The inoculation baseline will be defined as the last available assessment prior to administration of the malaria challenge agent. The IMP baseline will be defined as the last available assessment prior to the administration of the IMP. Unscheduled visits will be excluded from summary tables. Assessments conducted at Early Termination will be excluded from summary tables.

9.4.2 ANALYSIS OF THE PRIMARY ENDPOINT

The primary endpoint is the PK/PD relationship of MMV367. The basic PK/PD relationship will link the parasite clearance rate to the MMV367 blood concentration with a sigmoidal E_{max} model characterized by the E_{max} , EC_{50} and Hill coefficient parameters. If needed, alternative models will be applied, for instance to account for a lag in the drug response, which will contain additional parameters. The parameters will be estimated using a non-linear mixed-effect modelling of MMV367 concentration-time and parasitaemia-time profiles. First, a population PK model will be constructed with the measured concentrations; it will allow the individual PK parameters obtained and the full PK profile for each individual to be calculated. Second, the PD parameters will be estimated with the measured parasitaemia and the predicted individual PK profiles.

As a general concept the changes in living parasites in blood P are modelled as the effect of a net exponential growth rate GR and clearance rate $Kill$ due to MMV367 with an initial parasitaemia P_{base} at time t_0 (time of first observation). The equations are expressed in the log-scale such as:

$$\begin{aligned}\frac{dPL}{dt} &= GR - Kill \\ PL(t_0) &= PL_{base}\end{aligned}$$

where $PL = \ln(P)$ is the log-transformed parasite counts.

The effect of concentrations on parasite killing/clearance will be described as:

$$Kill = E_{max} \cdot \frac{C_c^{Hill}}{C_c^{Hill} + EC_{50}^{Hill}}$$

where C_c is the concentration in the central compartment, E_{max} is the maximum effect of the drug, EC_{50} is the concentration that results in 50% of the maximum effect and $Hill$ is the Hill coefficient.

Alternative models may be tested if the exploration of the data indicate a different behaviour, e.g. if a lag time is observed before the parasites are cleared, an effect compartment model will be tested.

Other key parameters such as the minimum inhibitory concentration (MIC), the minimal parasiticidal concentration (MPC₉₀), and the parasite reduction rate in 48 h (log₁₀PRR₄₈) will be derived from the PD model. The MIC is defined as the concentration at which parasite clearance by the drug equals the parasite growth, i.e., the MMV367 concentration at which the minimum parasite concentration is observed. It is calculated with the following equation in case of the E_{max} sigmoid model.

$$MIC = EC_{50} \left(\frac{GR}{E_{max} + GR} \right)^{1/Hill}$$

The MPC₉₀ is defined as the concentration at which the clearance effect is at 90% of the maximum. It is calculated as follows:

$$MPC_{90} = EC_{50} \cdot 9^{1/Hill}$$

The PRR₄₈ is defined as the parasite clearance achieved within 48 hours, usually given as the reduction of values on log₁₀ transformed scale. The maximum capacity of parasite clearance in 48 hours is determined as follows assuming that concentrations are maintained well above the MPC₉₀ for this time span.

$$PRR_{48} = 48h \frac{E_{max} - GR}{\ln(10)}$$

Full details of the modelling analysis will be described in the MAP.

PK and PD parameters will be tabulated as population estimates and relative standard error (RSE). The inter-individual variability (IIV) of PK parameters will be estimated. If the RSE of the PK parameters IIV is larger than that estimated from the FIH study, the FIH study will be used to help inform the IIV of the PK parameters. The IIV of PD parameters will be fixed to plausible values.

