Parasite regrowth following initial parasite clearance is required to effectively characterise PK/PD parameters such as the half maximum effective concentration (EC_{50}) of MMV367. A single dose of 20 mg is expected to result in initial parasite clearance in the IBSM model (\log_{10} parasite reduction ratio over a 48 h period [PRR_{48}] median 2.9, 95% CI: 0.26 - 5.8), but subsequent parasite regrowth is expected to occur. It is predicted that parasitaemia will return to the pre-dose baseline with a median of 7 days post-dosing (95% CI: 2.5 - 14). Additionally, modelling indicates that there is a 50% chance for a typical individual dosed with 20 mg to have a full parasitaemia profile above the lower limit of quantification (LLOQ) of the qPCR assay. Thus, a significant amount of data is expected to be generated at this dose level and three participants will be dosed with 20 mg MMV367 in Cohort 1.

Testing of 90 mg MMV367 is considered important because it is predicted to represent an “intermediate” dose level. That is, modelling indicates that 90 mg will result in faster parasite clearance (\log_{10} PRR_{48} median 3.6, 95% CI: 1.8 – 6.2) compared with 20 mg for a typical individual, while retaining a good chance of parasite regrowth occurring and thus contributing to refining the MMV367 EC_{50} estimate. Two participants will receive 90 mg MMV367 in Cohort 1.

Testing of 1500 mg MMV367 is required to characterise the PK/PD parameters across the full dose range, in particular the maximum killing rate (E_{max}). The chance of parasite regrowth occurring at this dose level is considered very low and thus data from this dose level will have a long duration of observable maximum killing rate ensuring a reliable estimation of the maximum clearance rate (E_{max}), however it is not anticipated to contribute to refining the estimate of the EC_{50} . Therefore, one participant dosed with 1500 mg is considered sufficient in the first cohort.

Dose selection for Cohort 2

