#### 10.4.3. *Building a PD model*

PD model development will be done using gradient based algorithms in IQRTools SysFit. The selected model will then be estimated with SAEM in Monolix to attempt to estimate IIV. Other appropriate methods may be used if advisable. As a general concept the changes in living parasite  $P$  are modeled as the effect of a net exponential growth rate  $GR$  and a killing or clearance rate  $Kill$  due to MMV367. The initial parasitemia  $P_{base}$  at time  $t_0$  will be derived from the mean parasitemia which was observed at treatment administration and a parameter  $PLerr$  to allow for population and individual deviations. The equations are expressed in the log-scale such as:

$$\begin{aligned}\frac{dPL}{dt} &= GR - Kill \\ PL(t_0) &= PL_{base} + PLerr\end{aligned}$$

where  $PL = \ln(P)$  is the log-transformed parasite counts.

Different models describing the relationship of MMV367 plasma concentration on the killing rate may be tested.

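### The protocol's MIC formula has Emax + GR where its own model requires Emax − GR, so the derived MIC is too low whenever an MIC exists

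*Protocol*

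**What the plan says.** Protocol section 9.4.2 sets dPL/dt = GR − Kill, where PL is the natural log of the parasite count. Kill is a sigmoid function of the central concentration with parameters Emax, EC50 and Hill, and "E_{max} is the maximum effect of the drug".

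The section names MIC among the key parameters to be derived from the PD model. In words: "The MIC is defined as the concentration at which parasite clearance by the drug equals the parasite growth". It adds that this is the concentration at which parasitaemia reaches its minimum. The formula then given for the sigmoid model is "MIC = EC_{50} \left(\frac{GR}{E_{max} + GR} \right)^{1/Hill}".

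A few lines later the maximum 48-hour reduction is given as "PRR_{48} = 48h \frac{E_{max} - GR}{\ln(10)}".

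The SAP (section 10.4.3) keeps the same GR − Kill structure but leaves the form of Kill open: "Different models describing the relationship of MMV367 plasma concentration on the killing rate may be tested". MIC appears in the SAP's abbreviation list. It has no formula anywhere in the SAP and is not among the PK/PD endpoints in section 10.5. The protocol defers full modelling details to the MAP, which is not among the documents reviewed.

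**The concern.** The MIC formula does not follow from the model and definition printed directly above it. Protocol section 9.4.2 calls MIC a key parameter of the primary analysis, and section 2.1 says the study's data will inform partner-drug selection and dosing considerations for later trials. An MIC that is biased low makes the drug look more potent than the fitted model says and overstates the time that concentrations stay above MIC. More participants would not reduce the bias, because it is in the formula and not in the estimation.

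**Working it through.** **Algebra.** Both statements of the definition (clearance equals growth; parasitaemia at its minimum) mean dPL/dt = 0, that is Kill = GR:

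- Emax·C^H / (C^H + EC50^H) = GR
- Emax·C^H = GR·C^H + GR·EC50^H
- C^H·(Emax − GR) = GR·EC50^H
- MIC = EC50·(GR/(Emax − GR))^(1/H), which exists only if Emax > GR.

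**Printed form put back into the model.** With C^H = EC50^H·GR/(Emax + GR), Kill = Emax·GR/(Emax + 2GR). This is less than GR for any positive GR, so parasites are growing at the printed MIC.

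**Numerical check.** Over 20,000 random parameter sets with Emax > GR > 0, the minus form satisfied Kill = GR to within rounding (largest relative error about 2×10^-15), and the plus form was too low in every set. One example, with Emax = 0.22/h, GR = 0.05/h, EC50 = 1 and Hill = 2:

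- root of Kill = GR: 0.542
- minus form: (0.05/0.17)^(1/2) = 0.542
- printed form: (0.05/0.27)^(1/2) = 0.430, which is 21% low.

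**Could Emax be a net rate?** If Emax already had growth subtracted, gross kill would be Emax + GR and the result would be EC50·(GR/Emax)^(1/Hill). That is not the printed form either, and it conflicts with the PRR48 formula, which subtracts GR from Emax. MPC90 = EC50·9^(1/Hill) is correct for the model as stated. MIC is the only derived formula that does not fit.

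**Size.** Printed/correct = ((Emax − GR)/(Emax + GR))^(1/Hill). The documents give no GR, Emax or Hill, so the following are assumptions:

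- GR: 2,800 viable parasites in an assumed 5 L of blood is 0.56/mL. Reaching 5,000/mL by Day 8 (192 h) gives ln(5,000/0.56)/192 = 0.0474/h. Blood volumes of 4 to 6 L give 0.046 to 0.048/h.
- Emax: from the PRR48 formula, Emax = log10PRR48·ln(10)/48 + GR. The inputs are the section 4.3 predictions: 20 mg, "median 2.9, 95% CI: 0.26 - 5.8"; 90 mg, "median 3.6, 95% CI: 1.8" to 6.2. Medians and upper limits are used.
- Hill: 1, 2 and 4, as examples.

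| log10 PRR48 | Emax (/h) | Printed/correct, Hill 1 | Hill 2 | Hill 4 | Kill/GR at printed MIC | Fold rise per 48 h |
|---|---|---|---|---|---|---|
| 2.9 | 0.187 | 0.595 | 0.771 | 0.878 | 0.66 | 2.15 |
| 3.6 | 0.220 | 0.646 | 0.804 | 0.896 | 0.70 | 1.98 |
| 5.8 | 0.326 | 0.746 | 0.864 | 0.929 | 0.77 | 1.67 |
| 6.2 | 0.345 | 0.758 | 0.871 | 0.933 | 0.78 | 1.63 |

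With a wider assumed GR of 0.04 to 0.07/h and the same four PRR48 values, the ratio is 0.50–0.79 at Hill 1, 0.71–0.89 at Hill 2 and 0.84–0.94 at Hill 4. The fold rise per 48 h is then 1.4 to 3.9.

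**The case against.** The algebra is not in dispute. The case on the other side concerns consequence and size.

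- **The MAP may hold the correct formula.** This stands: the plus form is the only MIC formula in the documents reviewed, not necessarily the only one in existence. If the MAP is right, protocol and MAP disagree and still need aligning.
- **The plus sign could come from reading the PDF by program.** This is possible and worth a look at the original page. The minus signs in the growth equation and in PRR48 were read correctly, so it is not a strong defence.
- **The fitted model is untouched.** This stands. MIC is computed after fitting, and a correct value can be recalculated from the reported parameters without new data. The formula also applies only if the sigmoid Emax model is kept.
- **No section says a dose is set from MIC.** This stands. Cohort 2 and 3 doses rest on PK/PD simulations, and simulating the differential equation does not use the closed-form MIC. Any effect on later dose choice is inference.
- **The percentages are weakly anchored.** This stands in part. The 2.9 is a prediction at 20 mg, where regrowth is expected, so treating it as maximal understates Emax and puts the 41% at the upper end for that GR. The protocol expects Day 8 parasitaemia above 5,000/mL, so GR could be higher, which enlarges the error. The direction and the symbolic ratio depend on none of this.

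**Conclusion.** The formula is wrong as written. It contradicts the protocol's own model, its verbal definition of MIC and its PRR48 formula, and no SAP section corrects it. The error is downward for every Emax > GR > 0; if Emax is not above GR, no MIC exists. The relative error shrinks as Emax/GR or Hill rises. Under the stated assumptions (GR about 0.047/h) it runs from 7% at Hill 4 to 41% at Hill 1. These percentages illustrate the size and are not estimates for MMV367. The damage is confined to one derived parameter, but the protocol calls that parameter key and the bias always favours the drug, so it should be corrected before any MIC is reported.

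**What to change.** In Protocol section 9.4.2, replace the equation with MIC = EC50·(GR/(Emax − GR))^(1/Hill) and add that it is defined only when Emax > GR. Check the original PDF page and the MAP, and bring the MAP into line if it carries the plus sign. If MIC is to be reported, state the same formula in SAP section 10.5. If another kill function is selected, define MIC there as the solution of Kill = GR. Recalculate any MIC already produced with the printed formula, if there is one.

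The cost is a one-line protocol clarification plus matching MAP and SAP wording. No data collection or model fitting changes. The reported MIC will be higher, and so less favourable, than the printed formula would give.
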